## **6.4 Enrollment**

Patients will be considered enrolled once informed consent is obtained per Institutional Review Board (IRB)/Ethics Committee (EC), the Indigo Aspiration Catheter has been inserted into the body as frontline treatment, and all eligibility is confirmed. Patients who fail to meet entry criteria will be considered a screen fail.

All follow-up visits will be conducted based on date of procedure, regardless of enrollment date.

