### **7.6.1 Adverse Events**

Adverse events (AE) must be recorded by the Investigator on the eCRFs and will be monitored during the entire study. All SAEs and procedure and device related AEs will be collected starting at Day 0 through final follow up for enrolled subjects. Additionally, bleeding complications should be reported.

Minimum requirements of data to be recorded are: event term, event start date, seriousness, action taken, outcome and device-relatedness or causality.

In order to ensure prompt reporting of AEs, all reportable AEs (as well as all related study data) are required to be entered into the EDC in a timely manner. Any suspected Unanticipated Adverse Device Events (UADEs)/ Unanticipated Serious Adverse Device Effects (USADE) should be reported immediately by calling the Sponsor. All device related Serious Adverse Events (SAEs) should be reported in the EDC within 72 hours of the site staff first being made aware of the occurrence of the SAE. If the EDC is unavailable, an email can be sent to Penumbra.

The Investigator must report adverse events to the IRB/EC according to local requirements. The Investigator is responsible for reporting time frames and complying with local or national requirements. In addition, the Investigator will report to the sponsor and IRB/EC any device malfunctions that could have led to a SAE, if required by national regulations or by local authorities.

For the purpose of reporting within this protocol, pre-existing conditions or planned procedures for pre-existing conditions are not reportable as AEs unless there is worsening of the condition with an increase in severity or frequency during the course of the study. All deaths will be reported regardless of causality. When reporting a death, the primary condition or diagnosis that contributed to the fatal outcome should be reported as a SAE with an outcome of death. Only a single cause

of death should be reported in EDC. If the cause of death is unknown, report “unknown cause of death” as a SAE.

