### 7.6.4 Protocol Deviation

Deviations defined in this protocol should be clearly documented, if identified during monitoring or through other means. For this study, deviations should be reported for the following categories:

- Inclusion/exclusion criteria deviation(s)
- Informed consent deviation(s)

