### **10.5.2 Screen Failure**

Screen failure subjects are all subjects considered for participation in the study, who failed to meet inclusion criteria or met exclusion criteria. Patients can be screen failed based on general criteria. These patients may or may not have signed an informed consent form.

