### **10.5.3 Enrolled**

An eligible patient is considered enrolled once informed consent is obtained and Indigo Aspiration System has been inserted into the body.

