6.5 Early Termination

Early termination subjects are all subjects who were enrolled but did not complete follow-up and were not known to have died. The early termination subject metric will be provided for 365 Day follow-up.

7 Definition of Analysis Population

All performance and safety outcome measures will be analyzed under the intent-to-treat (ITT) principle. Under this principle, the ITT sample includes all subjects who are enrolled. This population is the primary analysis population.

A per-protocol (PP) sample is defined as a subset of the ITT sample. The per-protocol sample will include all subjects that do not have major protocol deviations (eg. eligibility violation or informed consent violations). In addition to the ITT, a per protocol analysis will be done for the primary and secondary endpoints.

8 Statistical Analysis

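### Both documents contradict themselves on whether a consented, treated patient later found ineligible is a screen failure or stays in ITT

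*Protocol*

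**What the plan says.** One group of statements ties enrolment to eligibility:

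- Protocol 6.4 requires consent, the catheter "inserted into the body as frontline treatment, and all eligibility is confirmed". It continues: "Patients who fail to meet entry criteria will be considered a screen fail".
- Protocol 10.5.3: "An eligible patient is considered enrolled once informed consent is obtained and Indigo Aspiration System has been inserted into the body". SAP 6.3 is almost the same and also begins from an eligible patient.
- Protocol 10.5.2 and SAP 6.2 define screen failures as all those considered for the study "who failed to meet inclusion criteria or met exclusion criteria". Both set no time limit and add: "These patients may or may not have signed an informed consent form".

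A second group assumes that ineligible subjects can be enrolled:

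- Protocol 6.5 dates enrolment at the later of consent and catheter introduction. That sentence has no eligibility term.
- Protocol 7.6.4 makes breaches of the inclusion or exclusion criteria a reportable category of deviation.
- SAP 7 forms the per-protocol set as a subset of ITT: "The per-protocol sample will include all subjects that do not have major protocol deviations (eg. eligibility violation or informed consent violations".

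Two things depend on which group governs. ITT, the primary analysis population (Protocol 10.6.1, SAP 7), is every enrolled subject. Routine safety collection has the same scope (Protocol 7.6.1): "All SAEs and procedure and device related AEs will be collected starting at Day 0 through final follow up for enrolled subjects".

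**The concern.** Take a patient who has consented, has been treated with Indigo and is then found to fail an entry criterion. Under the first group of statements this is a screen failure, outside the primary limb-salvage rate and outside the routine SAE and device-related AE rates. Under the second group it is an enrolled subject with a deviation, inside both. Neither document says when confirmation of eligibility becomes final, so a site or the sponsor could class the same patient either way, possibly after limb status is known. The question arises whether consent came before or after the procedure.

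In a single-arm study the primary result is one proportion set against a fixed threshold, so a rule on who enters the denominator matters. The three sensitivity analyses in SAP 11 deal with missing 30-day data and loss to follow-up among enrolled subjects. They would not bring back a treated patient classed as a screen failure. On the literal definitions, ITT and per-protocol also cannot differ on eligibility, which is one of the two kinds of deviation that SAP 7 names. The per-protocol analysis would then differ from ITT only on consent violations or other major deviations.

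**Working it through.** **1. The statements side by side, for a patient consented, treated and later found ineligible**

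| Source | Enrolled? | In ITT? |
|---|---|---|
| Protocol 6.4, 10.5.2, 10.5.3 | No, screen failure | No |
| SAP 6.2, 6.3 | No, screen failure | No |
| Protocol 6.5, point of enrolment | Yes | Yes |
| Protocol 7.6.4 | Implied yes, as a deviation | Implied yes |
| SAP 7, per-protocol definition | Implied yes | Yes, and removed only from per-protocol |

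Both documents appear on both sides, so the conflict lies within each one.

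**2. The plan's own figure**

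Inputs from SAP 3: threshold 0.957 − 0.10 = 0.857, assumed rate 0.94, n = 115, one-sided alpha 0.025. With null variance for the critical value and alternative variance for the sampling distribution:

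- 1.96 × √(0.857 × 0.143 / 115) = 0.0640
- √(0.94 × 0.06 / 115) = 0.0221
- Power = Φ((0.083 − 0.0640) / 0.0221) = 0.805, as SAP Table 1 states.

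The planned sample size and power are not affected by this point.

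**3. Near-threshold illustration**

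SAP 8.1 requires p − 1.96 × √(p(1 − p)/n) > 0.857. Take 130 treated with complete data:

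| Salvaged / analysed | Rate | Lower limit | Endpoint |
|---|---|---|---|
| 118/130 | 0.908 | 0.858 | met |
| 117/130 | 0.900 | 0.848 | not met |
| 117/128 | 0.914 | 0.866 | met |

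The third row is the second with two of its 13 limb losses reclassified as screen failures.

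**4. Range**

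The documents give neither the number of such patients (k) nor their salvage rate, so both are assumed. Eligible patients are taken at 94% salvage, with 130 treated. Entries are exact binomial probabilities of meeting the SAP 8.1 rule.

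| k | All analysed, ineligible at 94% | All analysed, ineligible at 70% | All analysed, ineligible at 50% | Ineligible dropped |
|---|---|---|---|---|
| 2 | 0.951 | 0.930 | 0.910 | 0.916 |
| 4 | 0.951 | 0.903 | 0.849 | 0.924 |
| 6 | 0.951 | 0.870 | 0.767 | 0.930 |
| 13 | 0.951 | 0.708 | 0.383 | 0.907 |

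At 94% salvage, dropping them lowers the chance of success at every count shown. At 70% it lowers it for two patients and raises it from four upwards in this table. At 50% it raises it at every count, only slightly for two. For two patients at 70%, the expected rate does rise by dropping them, from (128 × 0.94 + 2 × 0.70)/130 = 0.936 to 0.940. The chance of success still falls, because the rule allows 12 losses in 130 but only 11 in 128.

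**The case against.** The strongest reply is that the documents treat confirmation of eligibility as an act completed before treatment. Protocol 6.6 lists it among the baseline assessments, Table 2 marks the criteria only in the screening and baseline column, and Protocol 6.7 places the procedure after baseline assessment and imaging. Protocol 6.5 then fixes enrolment without mentioning eligibility, and late-found ineligibility is not among the withdrawal reasons in Protocol 12.2. On that reading the deviation category and the per-protocol definition fit together, and nobody is removed afterwards.

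This reading is available, and it defeats the stronger inference that a reader might draw from Protocol 6.4, namely that such patients leave ITT by rule. It does not settle the matter. The screen-failure definitions carry no cut-off. Frontline treatment with Indigo is itself an inclusion criterion and is met only at the procedure. Protocol 6.6 treats baseline imaging as giving an initial diagnosis, and Protocol 6.7.4 records angiography and lesion characteristics at the procedure. How often a criterion is first found unmet at that stage is not known.

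It is also fair to say that such patients would not be invisible. Protocol 6.1 requires a log of patients consented but not enrolled, with reasons. Protocol 8.4.3 opens screen-failure records to the sponsor. Reporting of unanticipated device events (7.6.1) and device deficiencies (7.6.3) is not expressly limited to enrolled subjects. So the inference that all safety information would be lost is not supported. What could be lost is the routine SAE and AE collection and the 30-day outcome, since the log asks for reasons and not outcomes.

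Finally, the illustration in step 3 is a chosen case: one salvage short of passing, no attrition although the plan allows about 10%, and both reclassified patients limb losses. That criticism stands.

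**Conclusion.** The contradiction is real and sits inside each document. The status of a treated, consented patient later found ineligible is undefined, for ITT and for routine AE collection alike. This is worth correcting because the literal rule would take treated patients out of the only primary endpoint and no planned analysis would restore them.

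Two further inferences are tempting and not supported. One is that the Protocol and the SAP disagree: the SAP repeats the eligibility condition in 6.3, and the Protocol itself expects eligibility deviations in 7.6.4. The other is that the primary result is biased towards success. Direction and size depend on an unknown number of patients and an unknown salvage rate. With eligible patients at 94%, dropping two at 70% salvage, or 2 to 13 at 94%, gives no gain in the chance of meeting the endpoint. Dropping four at 70% moves it from 0.903 to 0.924, and 13 at 70% from 0.708 to 0.907. The change from 84.8% to 86.6% shows only that two reclassifications can decide a result close to the threshold.

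**What to change.** - In Protocol 6.4 and 10.5.3 and SAP 6.3, define enrolled as consent obtained and the Indigo Aspiration Catheter inserted as frontline treatment. Conform Protocol 6.5, whose post-procedure consent provision for North America also refers to confirmed eligibility, so that the eligibility check remains an instruction to sites and not part of the definition of enrolment.
- In Protocol 10.5.2 and SAP 6.2, limit screen failure to patients without consent or without catheter insertion.
- State in both documents that ineligibility found after the point of enrolment is a deviation. The subject stays in ITT, follow-up and AE collection, and is removed only from the per-protocol set.
- Report the number of any treated patients classed as screen failures, with reasons.

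The cost is wording in a handful of definitions. The entry criteria, sample size and power do not change. The downside is that the ITT rate may be slightly less favourable and that a few ineligible subjects need follow-up.

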## **6.5 Informed Consent**

The Investigator or designee will obtain written informed consent from the subject or the subjects' representative (e.g. LAR, next of kin, etc.) using the current Institutional Review Board (IRB)/Ethics Committee (EC) approved consent form per IRB/EC policy.

For sites in North America, patients who have had a procedure (using the Indigo Aspiration System with the Indigo Aspiration Catheter as frontline) and all eligibility is confirmed, may be consented up to 2 calendar days post-procedure but prior to initial discharge, and enrolled in the study. The point of enrollment is defined as the date of informed consent or introduction of the Indigo Aspiration Catheter, whichever occurs later.

For sites in Europe, the informed consent process will be applied per local Ethics Committee approvals.

All informed consent documents used under this protocol will be consistent with applicable elements of Good Clinical Practice (ICH E6), ISO 14155, Clinical investigation

of medical devices for human subjects – Good Clinical Practice (GCP), FDA 21 CFR Part 50 Protection of Human Subjects, and will be approved by the site's reviewing IRB/EC prior to study initiation.

Any modification to the sample informed consent form made by the study site must be approved by the Sponsor and the IRB/EC before use. Each study site will provide the Sponsor with a copy of the IRB/EC approved consent forms. Informed consent completion will be monitored regularly by the Sponsor.

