### 5.2 Exclusion Criteria

1. Life expectancy  $<1$  year
2. Target vessel size  $<2$  mm
3. LE ALI secondary to dissections, vasculitis and/or target vessel trauma
4. Amputation in the ipsilateral limb
5. Pregnancy or positive pregnancy test according to site specific standards of care (only required for women of childbearing potential, serum or urine acceptable)
6. Absolute contraindication to contrast administration
7. Patient is unwilling or unable to comply with protocol follow up schedule and/or based on the Investigator's judgment the patient is not a good study candidate

8. Currently participating in an investigational drug or device clinical trial that may confound the study endpoints. Patients in observational, natural history, and/or epidemiological studies not involving intervention are eligible.
9. Target thrombus in a saphenous vein bypass graft

[figure not shown]

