## **6 Study Procedures**

### **6.1 Overview of Study Flow**

Patients presenting with LE ALI should be assessed for eligibility. All sites will keep a screen failure log of all potential study candidates who are screened and not enrolled or screened, consented, and not enrolled. Reason(s) for exclusion will be recorded. Screening information, including screen failures, will be reported in Electronic Data Capture system (EDC).

Recruitment rates will be tracked over time for each site. The actual recruitment rates will be useful for planning further clinical studies and determining the widespread impact of the therapy.

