**Table 2: Schedule of Assessments**

ACTIVITY	Screening and Baseline Evaluation	Procedure (Day 0)	Discharge and/or 7 Days (whichever occurs first)	30 Day (± 14 days)	180 Day (± 30 days)	365 Day (± 60 days)
Written Informed Consent	X 					
Inclusion/Exclusion	X					
Medical History	X					
Pregnancy Test	X 					
Vital Signs	X		X	X	X	X
Rutherford Classification	X		X	X	X	X
Ankle-Brachial Index	X		X	X	X	X
DUS, CTA, or MRA	X			X	X	X
VascuQoL-6	X			X	X	X
Laboratory Assessments	X	X 				
Modified SVS Runoff Score and TASC II Score		X 				
Angiography		X 				
Procedure		X				
Adverse Event Review		X	X	X	X	X
Medication Review	X	X	X	X	X	X

 For US only, patients who have had an index procedure with the Indigo® Aspiration System and Aspiration Catheter used frontline, prior to informed consent, may be consented up to 2 calendar days post procedure but prior to discharge

 Only required for women of childbearing potential

 Laboratory assessments performed as part of standard of care

 Modified SVS Runoff Score will be required at multiple timepoints within the visit

 Angiography images must be uploaded to image management system for core lab review

 Modified SVS Runoff score is required for all subjects. TASC II score is only required when lesions are in the aortoiliac and/or femoropopliteal segments

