## **10.6 Definition of Analysis Populations**

### **10.6.1 Intent to Treat Sample**

As the primary analysis, all performance and safety outcome measures will be analyzed under the intent-to-treat (ITT) principle. Under this principle, the ITT sample includes all subjects who are enrolled. This population is the primary analysis population.

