8.1 Primary Endpoint Analysis

The primary endpoint is a safety endpoint consisting of the target limb salvage rate at 1-month (30 Day) post-procedure. Limb is considered salvaged if no amputation was performed on target limb within 30 Day post procedure, or if target limb was amputated at or distal to the tarsal/metatarsal joint. The primary safety analysis will be the difference between the study group and the combined historical control rate of 95.7% observed under current standards of care.

The null hypothesis is that the difference between the primary endpoint rate and the standard of care at 30 Day post-procedure is less than or equal to -10%. The alternative hypothesis is the difference at 30 Day post-procedure is greater than -10%. Formally, the null and alternative hypotheses to be tested are as follows:

$$H_0: P_{\text{study}} - 0.957 \leq -0.10$$

$$H_A: P_{\text{study}} - 0.957 > -0.10$$

Where P_{study} is the proportion of patients who achieve target limb salvage 30 Day post-procedure.

The primary safety endpoint is met if the lower limit of the two-sided 95% normal approximated confidence interval of the primary endpoint rate is greater than 85.7%. The primary safety analysis will be unadjusted.

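### Consent up to two days after the procedure can leave a treated patient with an early major amputation outside the primary analysis, and no planned analysis would show it

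*Protocol*

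**What the plan says.** - **Consent.** Protocol 6.5 provides that, at North American sites, patients already treated with Indigo as frontline and confirmed eligible "may be consented up to 2 calendar days post-procedure but prior to initial discharge". It adds: "The point of enrollment is defined as the date of informed consent or introduction of the Indigo Aspiration Catheter, whichever occurs later". European sites follow their local ethics approvals.
- **Scope.** Footnote 1 of Table 2 gives the same route a narrower reach: "For US only, patients who have had an index procedure".
- **Entry.** Protocol 6.4 makes enrolment depend on consent, catheter insertion and confirmed eligibility, and adds: "Patients who fail to meet entry criteria will be considered a screen fail". Exclusion 4 reads, in full, "Amputation in the ipsilateral limb". Exclusion 7 includes the investigator's judgment that the patient is not a good candidate. Neither states the time at which it is assessed.
- **Analysis set.** Protocol 10.6.1: "the ITT sample includes all subjects who are enrolled". SAP section 7 says the same. It also defines a per-protocol set that drops subjects with eligibility or consent violations.
- **Endpoint.** SAP 8.1: "Limb is considered salvaged if no amputation was performed on target limb within 30 Day post procedure", or if the amputation was at or distal to the tarsal/metatarsal joint. Success requires the lower limit of a two-sided 95% normal-approximation interval to exceed 85.7%.
- **Records on patients not enrolled.** Protocol 6.1: "All sites will keep a screen failure log of all potential study candidates who are screened and not enrolled", with reasons. Adverse events are collected for enrolled subjects only (Protocol 7.6.1).

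**The concern.** The 30-day clock starts at the procedure, but on the post-procedure consent route a patient enters the analysis set only at consent. Major amputations in that gap are already known when the patient is, or is not, approached. A patient who loses the limb on day 0 to 2 and is not then consented was treated with the device, had the event that the primary endpoint counts, and appears in no analysis.

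The entry criteria add to this. Read after the procedure, a major amputation of the treated leg literally meets exclusion 4, and exclusion 7 leaves room for judgment. So the primary failure event could itself serve as a reason for screen failure.

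There is no concurrent control arm in which the same selection could occur and cancel. The rate is tested against a fixed goal, so selective loss of early failures moves it in one direction only. The missing-data analyses in SAP section 11 cover enrolled subjects lost to follow-up before day 30 and do not reach patients who never enrolled.

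**Working it through.** **Inputs.** Control rate 95.7% (SAP Appendix A: 7743/8092 = 0.9569). Margin 10 points, so the goal is 0.957 − 0.10 = 0.857. Assumed study rate 94% (108/115), N = 115 raised to 130, one-sided alpha 0.025 (SAP section 3). Success rule from SAP 8.1.

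**1. The plan's own figure.** Normal approximation with null variance:

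Power = Φ[(0.94 − 0.857 − 1.96·√(0.857·0.143/115)) / √(0.94·0.06/115)] = Φ[(0.083 − 0.0640)/0.0221] = 0.805.

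This agrees with SAP Table 1. The point does not dispute it.

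**2. Pass threshold under the planned rule.** Lower limit = p − 1.96·√(p(1 − p)/n) > 0.857. The smallest passing results are 105/115 (at most 10 losses) and 118/130 (at most 12 losses).

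**3. Adding back k treated but unenrolled limb losses.** The documents do not give k, so it is an assumption. The numerator stays and the denominator grows by k.

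| Result | k | Rate | Lower limit | Goal met? |
|---|---|---|---|---|
| 108/115 | 0 | 93.9% | 89.5% | yes |
| 108/118 | 3 | 91.5% | 86.5% | yes |
| 108/119 | 4 | 90.8% | 85.6% | no |
| 105/116 | 1 | 90.5% | 85.2% | no |
| 118/131 | 1 | 90.1% | 85.0% | no |

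The last two rows start from the threshold results 105/115 and 118/130.

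**4. Chance of declaring success at a true rate of 85.7%.** If a share w of all limb losses is never enrolled, the enrolled rate is p/(p + (1 − p)(1 − w)). For w = 10% this is 0.857/(0.857 + 0.143·0.9) = 86.9%; for w = 20% it is 88.2%. Exact binomial probabilities of reaching the step 2 thresholds:

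| w (assumed) | N = 115 | N = 130 |
|---|---|---|
| 0 | 5.0% | 5.8% |
| 5% | 7.2% | 8.4% |
| 10% | 10.1% | 11.9% |
| 20% | 19.1% | 22.7% |
| 30% | 33.3% | 39.0% |

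The first row exceeds 2.5% because of the normal-approximation rule itself, not because of consent timing. Only the rise down each column belongs to this point.

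**5. If the true rate is 94%.** The enrolled rate moves to 94.6% (w = 10%), 95.1% (20%) or 95.7% (30%).

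**6. Deaths.** Under SAP 8.1 a patient who dies with no major amputation is not a limb loss. Adding three such deaths back as salvaged gives 111/118 = 94.1%, against 108/115 = 93.9%. Leaving them out does not raise the primary rate. It lowers the estimated 12-month mortality, a secondary endpoint.

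**The case against.** - **Eligibility belongs to baseline.** Protocol 6.5 attaches the two days to consent. Section 6.6 lists the eligibility check among baseline assessments, 6.7 puts the procedure after baseline, and Table 2 marks inclusion/exclusion only at screening and baseline. A reader might infer that eligibility too may be settled up to two days later. The documents do not say so, and the natural reading is a pre-procedure check. What remains is that no passage closes exclusions 4 and 7 before insertion, while 6.4 makes confirmed eligibility a condition of enrolment. The wording permits the problem without creating it outright. Even with eligibility fixed, a patient who is never consented is still not enrolled.
- **Early deaths.** A reader might infer that early deaths, or clinical worsening, also inflate limb salvage when they go unenrolled. SAP 8.1 does not support this: neither is a primary failure without a major amputation.
- **Safeguards.** A representative may consent, so an amputated or incapacitated patient can still be enrolled. Non-enrolment is logged with reasons, screen-failure records are open to sponsor review (Protocol 8.4.3), and SAP section 6 counts screen failures. These make the loss traceable in part, but no analysis uses them, and the log requires reasons rather than outcomes.
- **Size.** Reversing 108/115 takes four unenrolled losses beside seven observed, that is 4 of 11, or 36% of all limb losses, before consent and on the late-consent route. That is a demanding scenario and the objection stands. It is weaker near the threshold, where one loss suffices.

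**Conclusion.** The point holds in a limited form. With the plan followed as written, a major amputation between the procedure and consent can fall outside the intention-to-treat set, the bias on 30-day limb salvage is upward, and nothing planned would reveal it.

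The bias is possible, not established. Its size depends on the share of limb losses at sites using late consent, how many occur before consent, and how often such patients are then not enrolled. The documents give none of these. If 10–20% of limb losses went unenrolled, the chance of success at a true 85.7% would rise from 5.0% to 10–19% (N = 115) or from 5.8% to 12–23% (N = 130). If the true rate is near 94%, the effect on the estimate is about 1 point or less over the same range. All these figures use the normal-approximation interval that the SAP specifies; an exact interval would be a different rule.

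Separately, 6.5 and Table 2 disagree on who may use the route. This matters for the per-protocol set, because a late-consented subject from a North American site outside the US would be compliant under one passage and a consent violation under the other. The documents do not say whether such sites exist.

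**What to change.** 1. **Protocol 5.2 and 6.4.** State that eligibility, including exclusions 4 and 7, is judged on the patient's status before catheter insertion, and that later events are not grounds for screen failure.
2. **SAP 8.1 and section 11.** From the existing screening log, report how many patients treated with Indigo as frontline were not enrolled, and why. Add a sensitivity analysis that counts logged pre-consent major amputations as limb losses, with a worst case that also counts treated, unenrolled patients of unknown limb status as losses. Report logged deaths under mortality, not as primary failures.
3. **Protocol 6.5 and Table 2, footnote 1.** Reconcile the two statements of where post-procedure consent applies.

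A table of the primary rate by consent before or after the procedure is optional and descriptive only, since it cannot show patients who never enrolled.

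Post-procedure consent itself can stay. The cost is a few sentences of wording and a little extra analysis. Because the log need not hold limb status, some patients may enter only the worst case unless ethics rules allow that item to be recorded. The bounding rate may also be less favourable than the primary one.
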